9.4.2. Efficacy Analysis

Response Evaluable Set will be used for all response related analyses including ORR, DCR, DOR, PFS, and TTP, and OS.

Tumor response will be presented in the form of participant data listings that include, but are not limited to tumor type, dose on Day 1, tumor response at each visit. In addition, progression date, death date, date of first response and last assessment date, and date of last contact will be listed. A summary of tumor response based on RECIST 1.1 will also be presented.

Progression date, date of first response, last tumor assessment date, date of last contact, and death date will be listed.

The Kaplan-Meier methods will be used to analyze all time to event efficacy endpoints. The efficacy endpoints that will be analyzed in this study are defined as follows:

- ORR is defined as the percentage of participants with a BOR of CR or PR.
- DCR is defined as the percentage of participants with a BOR of CR, PR, non-CR/non PD or SD.
- DOR is defined as the time from first documentation of CR or PR to date of first documentation of PD or death due to any cause, whichever occurs first.
- PFS is defined as time from start date of treatment to the date of first documentation of PD or death due to any cause.
- TTP is defined as the time from start date of treatment to the date of the first documentation of PD.
- OS is defined as the time from start date of treatment to the date of death due to any cause.

The detailed analyses will be described in the SAP. The definition of each response category is provided in [Appendix 11](#).

9.4.3. Pharmacokinetic Analysis

9.4.3.1. Single-Dose and Steady-State PF-07209960 Pharmacokinetic Analysis

Serum concentrations of PF-07209960 will be summarized descriptively (n, mean, standard deviation, coefficient of variation, median, minimum, maximum, geometric mean and its associated coefficient of variation) by dose, cycle, day and nominal time. Median profiles of the concentration-time profiles after C1D1 dose and C2D15 dose will be plotted separately by dosing cohort and cycle using nominal times for Patient 1 only. Median profiles will be presented on both linear-linear and log-linear scales.

Individual participant serum concentration-time data within a dose interval after C1D1 and C2D15 will be analyzed using noncompartmental methods to determine single- and multiple-dose PK parameters. Single-dose PK parameters to be estimated will include the Cmax, Tmax, and AUC from time 0 to AUC1last, and if data permit, AUC from time 0 extrapolated to AUCnr, t1/2, apparent oral Cl/F , and Vd. Multiple-dose PK parameters to be estimated will include Cmax,ss, Tmax,ss, AUCtau,ss, mean Ctrough,ss, CLs, and if data permit, Vz,ss,F, t1/2,ss, and Ra. The single dose and steady state PK parameters will be summarized descriptively (n, mean, standard deviation, coefficient of variation, median, minimum, maximum, geometric mean and its associated coefficient of variation) by dose level, cycle and day.

Dose normalized AUCinf (AUCtau,ss), AUC1last and Cmax will be plotted against dose (using a logarithmic scale) by cycle and day. These plots will include individual participant values and the geometric means for each dose.

9.4.4. Analysis of Immunogenicity Data

For the immunogenicity data, the percentage of participants with positive ADA and NAb will be summarized. Listings and summary tabulations of the ADA and NAb data at baseline and post-randomization will be generated. For participants with positive ADA or NAb, the magnitude (titer), time of onset, and duration of ADA or NAb response will also be described, if data permit. The potential impact of immunogenicity on PK and clinical response including pharmacodynamic markers, safety/tolerability and efficacy will be explored, if warranted by the data.

9.4.5. Tertiary/Exploratory Endpoint(s)

CCI

.

9.4.6. Other Safety Analyses

All safety analyses will be performed on the safety population.

Summaries and analyses of safety parameters will include all participants in the safety analysis set.

AEs, ECGs, BP, heart rate, and safety laboratory data will be reviewed on an ongoing basis during the study to evaluate the safety of participants. Any clinical laboratory, ECG, BP, and

PR abnormalities of potential clinical concern will be described. Safety data will be presented in tabular and/or graphical format and summarized descriptively, where appropriate.

Medical history and physical examination, as applicable, collected during the course of the study will be considered source data and will not be required to be reported, unless otherwise noted. However, any untoward findings identified on physical examination conducted during the active collection period will be captured as AEs, if those findings meet the definition of an AE. Demographic data collected at screening will be reported.

9.4.6.1. Electrocardiogram Analyses

Changes from baseline for the ECG parameters QT interval, heart rate, QTcF interval, PR interval, and QRS complex will be summarized by treatment and time.

The number (%) of participants with maximum postdose QTc values and maximum increases from baseline in the following categories will be tabulated by treatment:

Safety QTc Assessment

Degree of Prolongation	Mild (msec)	Moderate (msec)	Severe (msec)
Absolute value	>450-480	>480-500	>500
Increase from baseline		30-60	>60

In addition, the number of participants with uncorrected QT values >500 msec will be summarized.

If more than 1 ECG is collected at a nominal time after dose administration (for example, triplicate ECGs), the mean of the replicate measurements will be used to represent a single observation at that time point. If any of the 3 individual ECG tracings has a QTcF value >500 msec, but the mean of the triplicates is not >500 msec, the data from the participant's individual tracing will be described in a safety section of the CSR in order to place the >500-msec value in appropriate clinical context. However, values from individual tracings within triplicate measurements that are >500 msec will not be included in the categorical analysis unless the average from the triplicate measurements is also >500 msec. Changes from baseline will be defined as the change between the postdose QTcF value and the average of the time-matched baseline triplicate values on Day -1, or the average of the predose triplicate values on Day 1.

In addition, an attempt will be made to explore and characterize the relationship between plasma concentration and QT interval length using a PK/PD modeling approach. If a PK/PD relationship is found, the impact of participant factors (covariates) on the relationship will be examined.

The analysis of ECG results will be based on participants in the safety analysis set with baseline and on-treatment ECG data. Baseline is defined as a Cycle 1 Day 1 pre-dose.

ECG measurements (an average of the triplicate measurements) will be used for the statistical analysis and all data presentations. Any data obtained from ECGs repeated for

safety reasons after the nominal time-points will not be averaged along with the preceding triplicates. Interval measurements from repeated ECGs will be included in the outlier analysis (categorical analysis) as individual values obtained at unscheduled time points.

QT intervals will be corrected for HR (QTcF) using standard correction factors (ie, Fridericia's (default correction), Bazett's, and possibly a study-specific factor, as appropriate). Data will be summarized and listed for QT, HR, RR, PR, QRS, QTcF (and other correction factors, eg, QTcB as appropriate), and dose. Individual QT (all evaluated corrections) intervals will be listed by time and dose. The most appropriate correction factor will be selected and used for the following analyses of central tendency and outliers and used for the study conclusions. Descriptive statistics (n, mean, median, standard deviation, minimum, and maximum) will be used to summarize the absolute corrected QT interval and changes from baseline in corrected QT after treatment by dose and time point. Details of additional analysis (if any) will be specified in SAP.

9.4.6.2. Adverse Events

AEs will be graded by the investigator according to the CTCAE version 5.0 and coded using MedDRA, except CRS, which will be graded by ASTCT criteria ([Lee et al, 2019](#)). AE data will be reported in tables and listings. Summaries of AEs by mapped terms, appropriate thesaurus level, toxicity grade, and seriousness and relationship to study treatment will be presented, as well as summaries of AEs leading to death and premature withdrawal from study treatment. The number and percentage of participants who experienced any AE, SAE, treatment related AE, and treatment related SAE will be summarized according to worst toxicity grades. The summaries will present AEs both on the entire study period and by cycle (Cycle 1 and Cycles beyond 1). Listings of DLTs and deaths will be provided.

9.4.6.3. Laboratory Test Abnormalities

The number and percentage of participants who experienced laboratory test abnormalities will be summarized according to worst toxicity grade observed for each laboratory assay. The analyses will summarize laboratory tests both on the entire study period and by cycle (Cycle 1 and Cycles beyond 1). For laboratory tests without CTCAE grade definitions, results will be categorized as normal, abnormal, or not done.

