3. ENDPOINTS AND BASELINE VARIABLES: DEFINITIONS AND CONVENTIONS

3.1. Primary Endpoint(s)

3.1.1. Part 1

- *First cycle DLTs.*
- *AEs as characterized by type, frequency, severity (as graded by NCI CTCAE version 5.0; for CRS as graded by ASTCT criteria), timing, seriousness, and relationship to study therapy.*
- *Laboratory abnormalities as characterized by type, frequency, severity (as graded by NCI CTCAE version 5.0), and timing.*

3.1.2. Part 2

- *AEs as characterized by type, frequency, severity (as graded by NCI CTCAE version 5.0; for CRS as graded by ASTCT criteria), timing, seriousness, and relationship to study therapy.*
- *Laboratory abnormalities as characterized by type, frequency, severity (as graded by NCI CTCAE version 5.0), and timing.*
- *ORR as determined by RECIST version 1.1.*

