6.1.3. Laboratory abnormalities

- Analysis set: Safety analysis set
- Analysis methodology:

Laboratory abnormalities will be presented as tables and characterized by type, frequency, severity (as graded by NCI CTCAE version 5.0), and timing. For laboratory tests without CTCAE grade definitions, results will be categorized as normal, abnormal high/low, or not done. The number and percentage of participants who experienced laboratory test abnormalities will be summarized according to worst toxicity grade observed for each laboratory assay. Shift tables of baseline grade to worst post-baseline grade will be provided. Quantitative summaries for change from baseline and percent change from baseline for the laboratory tests may be provided, if deemed necessary. These summaries will be presented for the entire on-treatment period and for the various subgroups of the study (by dose level for Part 1 and by expansion cohort for Part 2).

Hematology, serology and coagulation lab results can be combined into one summary output. Separate summaries will be created for chemistiy tests. Urinalysis and pregnancy tests will not be summarized and will only be listed.

- Missing data: Missing lab values will not be imputed.

6.2. Secondary Endpoints for Part 1

CCI

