6.9.1. Adverse Events

AEs will be graded by the investigator according to the CTCAE version 5.0 and coded using MedDRA, except CRS, which will be graded by ASTCT criteria (Lee et al, 2019). AE data will be reported in tables and listings. Summaries of TEAEs by primary system organ class and preferred terms, toxicity grade, and seriousness and relationship to study treatment will be presented. In addition, summaries of adverse events leading to death, dose modification, dose interruption, and premature withdrawal from study treatment will be tabulated. The number and percentage of participants who experienced any AE, SAE, treatment related AE, and treatment related SAE will be summarized according to worst toxicity grades. The summaries will present AEs for the entire on-treatment period, by cycle for Part 1 (Cycle 1 and Cycles beyond 1), and for the various parts of the study (by dose level for Part 1 and by expansion cohort for Part 2). In the summary table for Part 1, a “Total” column, summarizing data across all dose levels, will be presented. Listings of AEs leading to dose modification, dose interruption, permanent discontinuation of the study treatment, and death will be provided. Listings of DLTs, deaths, and SAEs will also be provided. Death and SAE information will be based on the data captured from the CRF.

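### The SAP omits the Cycle 1 versus later-cycle laboratory summary that the protocol specifies, and is unclear on the same split for Part 2 adverse events

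*Protocol*

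**What the plan says.** Laboratory abnormalities are a primary endpoint of both parts. SAP 3.1 defines them under Part 1 and again under Part 2 as "Laboratory abnormalities as characterized by type, frequency, severity (as graded by NCI CTCAE version 5.0), and timing".

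For their analysis, Protocol 9.4.6.3 states: "The analyses will summarize laboratory tests both on the entire study period and by cycle (Cycle 1 and Cycles beyond 1". Protocol 9.4.6.2 has the parallel sentence for adverse events: "The summaries will present AEs both on the entire study period and by cycle (Cycle 1 and Cycles beyond 1". Neither sentence is restricted to a part.

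SAP 6.1.3 opens with a general promise: "Laboratory abnormalities will be presented as tables and characterized by type, frequency, severity (as graded by NCI CTCAE version 5.0), and timing". It then names its outputs. These are worst toxicity grade per assay, normal/abnormal/not-done categories for tests without CTCAE grades, and a shift table ("Shift tables of baseline grade to worst post-baseline grade will be provided"). Change from baseline is optional: "Quantitative summaries for change from baseline and percent change from baseline for the laboratory tests may be provided, if deemed necessary". On the period covered it says: "These summaries will be presented for the entire on-treatment period and for the various subgroups of the study", the subgroups being dose level in Part 1 and expansion cohort in Part 2. SAP 6.4.2 applies 6.1.3 to Part 2.

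For adverse events, SAP 6.9.1 says: "The summaries will present AEs for the entire on-treatment period, by cycle for Part 1 (Cycle 1 and Cycles beyond 1". SAP 6.4.1 says Part 2 adverse events are summarized as in Part 1 and points to SAP 6.1.2, which in turn refers to 6.9.1.

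**The concern.** The SAP keeps the neighbouring content of Protocol 9.4.6.3 (worst grade per assay, categories for ungraded tests) but puts a different period rule in place of the by-cycle sentence. A programmer working from the SAP would produce whole-period laboratory tables only.

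The split matters clinically. Thrombocytopenia and abnormal liver and renal function are listed as risks in Protocol 2.3.1 and as events of special interest in Protocol 8.3.8, and all are detected largely by laboratory tests. The DLT window is the first 28 days (Protocol 4.3.3), while Protocol 4.3.6 allows later related events to prompt re-evaluation of the MTD/RP2D. A worst grade over the whole on-treatment period cannot show whether an abnormality arose after the first doses or later.

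Sampling intensity also changes. As the schedule of activities reads after extraction, hematology and chemistry are taken on seven days in Cycle 1 (Days 1, 2, 3, 4, 8, 15 and 22) and on two days in each later cycle (Days 1 and 15). A pooled worst grade mixes a densely sampled period with sparsely sampled ones.

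**Working it through.** The plan gives no figure to reproduce, so the check is mainly of text.

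**Step 1. Compare the four primary safety summaries.**

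| Summary | Protocol | SAP |
|---|---|---|
| Laboratory, Part 1 | Whole period and by cycle (9.4.6.3) | Whole on-treatment period only (6.1.3) |
| Laboratory, Part 2 | Same (9.4.6.3) | Same as Part 1, so no cycle split (6.4.2 to 6.1.3) |
| Adverse events, Part 1 | Whole period and by cycle (9.4.6.2) | Whole on-treatment period and by cycle (6.9.1) |
| Adverse events, Part 2 | Same (9.4.6.2) | Unclear: 6.9.1 limits the split to Part 1; 6.4.1 says as in Part 1 |

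**Step 2. Look for the laboratory split elsewhere in the SAP.** Section 5.2 (general methods) sets grouping by dose level or cohort and says nothing on cycles. Section 6.9.5 adds a clinical-significance assessment but no cycle split. Section 3.5 defines two on-treatment periods, ending 28 or 90 days after the last dose (or the day before new anticancer therapy, if earlier). They differ only in their end, so neither separates Cycle 1 from later cycles.

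**Step 3. Ask whether any committed laboratory table carries time.** Worst grade, baseline-to-worst shift and normal/abnormal/not done are each one result per participant per test over the period. The optional change-from-baseline summary names no visits or cycles. Timing is therefore promised, but no committed table delivers it.

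**Step 4. What the whole-period figure leaves open.** Let p1 be the Cycle 1 risk, p2 the risk in each later cycle, and k the number of cycles, with complete follow-up. The whole-period proportion is P = 1 − (1 − p1)(1 − p2)^(k − 1). P alone does not determine p1: any value from 0 to P is compatible with it. With 5 of 20 participants affected (P = 25%), the number affected in Cycle 1 can be anything from 0 to 5.

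An illustration with assumed rates, since the documents give none, and k = 4:

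- Early pattern, p1 = 20% and p2 = 2%: P = 1 − 0.80 × 0.98³ = 24.7%; 30 × 0.247 = 7.4 participants.
- Constant pattern, 7% per cycle: P = 1 − 0.93⁴ = 25.2%; 30 × 0.252 = 7.6 participants.

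The two look alike in a cohort of 30, although Cycle 1 risk differs nearly three-fold (20/7 = 2.9). The near-tie depends on k:

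- k = 2: 1 − 0.80 × 0.98 = 21.6%, against 1 − 0.93² = 13.5%.
- k = 6: 1 − 0.80 × 0.98⁵ = 27.7%, against 1 − 0.93⁶ = 35.3%.

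The illustration shows only that a cumulative worst grade hides when events occurred. It does not predict this trial's data.

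**The case against.** Several stronger readings are tempting, and the documents do not support them.

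A reader might infer that no laboratory timing table is planned at all. SAP 6.1.3 explicitly says its tables will characterize timing, and Protocol 9.4.6.3 still calls for the by-cycle summary. What stands is that the SAP specifies no table that does this.

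A reader might infer that the Part 2 adverse-event split has been deleted. SAP 6.4.1, followed literally through 6.1.2 to 6.9.1, could carry the Part 1 split into Part 2; the Part 1 wording of 6.9.1 points the other way. This is a conflict within the SAP, not a clean omission.

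A reader might infer that the SAP simply overrides the protocol. Protocol Section 9 does let the SAP modify planned analyses where appropriate, but it also requires a protocol amendment for major modifications of primary endpoint analyses. SAP Section 2 describes the SAP as adding detail to the analyses the protocol outlines. Silence in the SAP may be a drafting slip and does not clearly cancel Protocol 9.4.6.3. Equally, the permission to modify does not excuse a change that is neither declared nor justified.

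A reader might infer that RP2D selection is compromised. First-cycle toxicity enters through DLTs, which are listed with start and stop day relative to the first dose (SAP 6.1.1), and through the BLRM (SAP 5.1). Dose-level review considers all available laboratory results (Protocol 9.6), and late related events are reviewed under Protocol 4.3.6. Laboratory abnormalities meeting the criteria in Protocol 10.3.1 are also recorded as adverse events, which in Part 1 are split by cycle. These safeguards limit the consequence. They do not supply the missing laboratory summary.

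**Conclusion.** The concern holds in a limited form. The protocol's by-cycle laboratory summary is absent from the SAP in both parts, and no laboratory table the SAP commits to conveys timing, an attribute of a primary endpoint. For Part 2 adverse events the SAP is internally inconsistent. The text at issue is complete, so redaction does not explain either point.

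The consequence is confined to descriptive safety reporting. The study has no formal hypothesis testing, and dose decisions draw on other sources. Within that reporting, a whole-period proportion P is compatible with any Cycle 1 proportion from 0 to P. The textual conclusion does not depend on the assumed rates. Whether the removal counts as a major modification needing a protocol amendment is a matter of judgement that the documents do not settle.

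**What to change.** In SAP 6.1.3, and so in 6.4.2, present the worst-grade laboratory summary for Cycle 1, for Cycles beyond 1 and for the entire on-treatment period, by dose level in Part 1 and by expansion cohort in Part 2. In SAP 6.9.1, extend the cycle split from Part 1 to Part 1 and Part 2, so that it agrees with SAP 6.4.1 and Protocol 9.4.6.2. If the sponsor did mean to remove the laboratory split, the SAP should say so, give the reason, and address the amendment condition in Protocol Section 9.

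Two additions are useful but go beyond the protocol and are optional: shift tables by period, and period-specific denominators (participants with a post-baseline value of that test in the period).

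The cost is two short SAP edits and a few extra runs of existing table programs. No new data are needed.

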9.4.7. Other Analyses

Pharmacogenomic or biomarker data from Banked Biospecimens may be collected during or after the trial and retained for future analyses; the results of such analyses are not planned to be included in the CSR.

9.4.7.1. Analysis of Biomarker Endpoints

For blood and biopsy samples, summary statistics (eg, the mean and standard deviation, median, and minimum/maximum levels of continuous, and frequencies and percentages of categorical biomarker measures) will be determined at baseline and post-treatment (if available). Further analysis will be specified in the SAP.

Clinically relevant and interpretable biomarker assessments generated for Primary and Secondary objectives will be summarized in the CSR. Results from exploratory endpoint analyses will be reported in the CSR or will be disclosed to the scientific community through publication(s) at scientific conferences and/or in peer-reviewed scientific journals. Given the exploratory nature of exploratory objectives and endpoints, the associated data analyses may not be complete at the time of CSR authoring.

9.4.7.2. Population Pharmacokinetic Analysis or PK/PD Modeling

PF-07209960 PK and pharmacodynamic data from this study may be analyzed using population modeling approaches and may also be pooled with data from other future studies to investigate any association between PF-07209960 exposure and biomarkers or selected safety and/or efficacy endpoints. The results of these analyses, if performed, may be reported separately from the clinical study report.

9.5. Interim Analyses

No formal interim analysis will be conducted for this study. As this is an open-label study, the sponsor may conduct unblinded reviews of the data during the course of the study for the purpose of safety assessment, facilitating dose-escalation decisions, facilitating PK modeling, and/or supporting clinical development.

9.6. Data Monitoring Committee or Other Independent Oversight Committee

This study will not use a DMC. However, a DLRM will convene for dose escalation decisions. The actual dose selected at each dose decision may be at or below the model's recommended dose as determined by the members of the DLRM after considering all safety information. The review team will be composed of investigator(s), Pfizer GCL, Pfizer Study Clinician, and Pfizer study manager. Additional members may be added as needed (eg, Clinical Pharmacologist Lead, Translational Oncology, Safety Risk Lead or designee and Pfizer Biostatistics representative). A quorum, defined as >50% of the participating investigators or their qualified designee (ie, subinvestigator or research nurse or study coordinator possessing hard copy documentation [eg, email] of the investigator's vote regarding the dose level review), must be in attendance for the DLRM. The DLRM will be rescheduled if a quorum is not reached.

Voting members of the DLRM will include the Pfizer medical monitor, the Pfizer Safety Risk Lead or designee, and all participant investigators or their qualified medical doctor designee(s). The team may recommend escalation to the next planned dose, escalation to an intermediate dose (a dose lower than the next planned dose), continuation or delay in dosing, repetition or expansion or a cohort, de-escalation at a lower dose, or termination of the study.

All available study day including demographics, medical history (including tumor history), concomitant medications, AEs, ECGs, vital signs, laboratory results, and emerging PK or PD data will be reviewed. Data to be reviewed may be unqueried.

